1. BACKGROUND

Bladder cancer is the ninth most common cancer in the world (World Cancer Research Fund International 2016). In 2012, an estimated 14.1 million people worldwide had bladder cancer, of whom 330,380 were newly diagnosed; in the same year, 123,051 deaths were attributable to the disease (International Agency for Research on Cancer 2016; World Cancer Research Fund International 2016). In the United States, estimates are that 76,960 new cases of bladder cancer will be diagnosed in 2016 (about 58,950 in men and 18,010 in women), and 16,390 deaths will occur due to the disease (American Cancer Society 2016).

This study is being conducted to evaluate the safety of atezolizumab as second-line treatment for locally advanced or metastatic urothelial or non-urothelial carcinoma of the urinary tract. The study will also evaluate treatment efficacy and explore potential tumor biomarkers related to atezolizumab.

The aim of the Statistical Analysis Plan (SAP) for independent Data Monitoring Committee (iDMC) is to state the scope and extent of iDMC analyses.

This SAP is based on the Study Protocol MO29983:

- version 1.0, 21 Jul 2016
- version 2.0, 25 Aug 2016
- version 3.0, 23 Nov 2016
- version 4.0, 31 Jan 2017 (Canada only)
- version 5.0, 19 May 2017
- version 6.0, 06 Jul 2017 (Canada only)
- version 7.0, 22 Feb 2018
- version 8.0, 07 Mar 2018 (Canada only)
- version 9.0, 08 Oct 2018
- version 10.0, 08 Oct 2018 (Canada only)
- version 11.0, 22 Oct 2019
- version 12.0, 22 Oct 2019 (Canada only)
- version 13.0, 03 Mar 2021
- version 14.0, 04 Mar 2021 (Canada only)
- version 15.0, 17 Dec 2021
- version 16.0, 17 Dec 2021 (Canada only)

2. STUDY DESIGN

Study MO29983 is an open label, single-arm, multicenter study of the safety of atezolizumab as second-line treatment for patients with locally advanced or metastatic urothelial or non-urothelial carcinoma of the urinary tract. The study includes evaluation of the efficacy of atezolizumab and potential tumor biomarkers associated with atezolizumab.

Study screening will take place within 28 days prior to initiation of study treatment. Eligible patients will be enrolled and begin treatment with 1200 mg atezolizumab intravenous (IV) every 3 weeks. The single agent study treatment will continue until investigator-assessed loss of clinical benefit, unacceptable toxicity, investigator or patient decision to withdraw from therapy, or death (whichever occurs first).

During the study treatment period, patients will be followed for safety based on adverse event (AE) assessments including vital signs, physical findings and clinical laboratory test results. Efficacy will be evaluated by the investigator according to both Response Evaluation Criteria in Solid Tumors (RECIST) v1.1 and modified RECIST. Exploratory biomarker analyses will be conducted based on primary tumor tissue or biopsied metastatic tumor tissue collected at baseline and an optional tumor sample collected at the second study treatment cycle.

Following discontinuation of study treatment, safety assessments will be conducted 30 days after the last study drug administration or until initiation of other anti-cancer therapy (whichever occurs first). Thereafter, patients will be followed for disease progression (unless this has already occurred), serious adverse events (SAEs), AEs of special interest, anti-cancer therapy and survival. Follow-up will continue for up to four years after the last patient is enrolled in the study.

2.1 PROTOCOL SYNOPSIS

The Protocol Synopsis is provided in Appendix 1. For Appendix 1 additional details, see the Schedule of Assessments in Appendix 2.

2.2 OUTCOME MEASURES

The primary objective of this study is to evaluate the safety of atezolizumab. The secondary objectives of the study include evaluation of the efficacy of atezolizumab. Additional secondary study objectives include the evaluation of efficacy of atezolizumab according to patient-reported outcomes (PROs).

2.2.1 Primary Efficacy Outcome Measures

Not applicable for this study.

2.2.2 Secondary Efficacy Outcome Measures

The following endpoints are defined to evaluate efficacy:

- Overall survival (OS), defined as the time from initiation of study treatment to death from any cause.
- Progression-free survival (PFS), defined as the time from initiation of study treatment to the first occurrence of disease progression or death from any cause, whichever occurs first. PFS will be calculated based on disease status evaluated by

investigator according to RECIST v1.1 and also by disease status evaluated by the investigator according to modified RECIST

- Overall response rate (ORR), defined as the proportion of patients with a best overall response of either complete response (CR) or partial response (PR). ORR will be calculated based on disease status evaluated by investigator according to RECIST v1.1 and also by disease status evaluated by the investigator according to modified RECIST
- Disease control rate (DCR), defined as the sum of the CR, PR and stable disease (SD) rates. DCR will be calculated based on disease status evaluated by investigator according to RECIST v1.1 and also by disease status evaluated by the investigator according to modified RECIST
- Duration of response (DoR), defined as the time from first occurrence of a documented response to disease progression or death from any cause, whichever occurs first. Duration of response will be calculated based on disease status evaluated by investigator according to RECIST v1.1 and also by disease status evaluated by the investigator according to modified RECIST

Additional secondary study objectives include the evaluation of efficacy of atezolizumab to the following PROs:

- Change from baseline in health-related quality of life (HRQoL), as assessed using the EORTC Quality-of-Life Questionnaire Core 30 (QLQ-C30).
- EuroQol EQ-5D-5L-assessed utility.

2.2.3 Exploratory Efficacy Outcome Measures

Not applicable for this study.

2.2.4 Pharmacokinetic Efficacy Outcome Measures

Not applicable for this study.

2.2.5 Safety Outcome Measures

The following endpoints are defined to evaluate safety:

- Nature, severity, duration, frequency and timing of AEs.
- Changes in vital signs, physical findings, and clinical laboratory results during and following atezolizumab administration.

2.3 DETERMINATION OF SAMPLE SIZE

This is a single-arm safety study. There is no formal statistical hypothesis and all analyses will be descriptive. The results for the primary safety variables will be presented via percentages and corresponding 95% Clopper-Pearson confidence intervals (CIs).

A sample size of approximately 1000 patients is planned for this study. The precision of (e.g., rare) AE incidence estimates presented by two-sided exact 95% Clopper-Pearson CIs are shown in Table 1.

Table 1 Two-Sided Clopper-Pearson 95% Confidence Intervals for Adverse Event Rate Estimates

Number of Patients with at Least One Event (Expected) N=1000	Expected Event Rate (%)	Lower limit of CI (%)	Upper limit of CI (%)
12	1.2	0.62	2.09
10	1.0	0.48	1.83
8	0.8	0.35	1.57
6	0.6	0.22	1.3
5	0.5	0.16	1.16
4	0.4	0.11	1.02
3	0.3	0.06	0.87
2	0.2	0.02	0.72
1	0.1	0.00	0.56

CI = confidence interval.

Therefore, for a sample size of 1000 patients and an expected AE incidence of 0.5%, based on the half-width of the Clopper-Pearson 95% CI, the true AE rate can be estimated with a precision of: $\pm(1.16\% - 0.16\%)/2\% = \pm0.5\%$.

2.4 ANALYSIS TIMING

The primary analysis will occur 6 months after the last patient has been enrolled.

The final analysis will occur at the end of the study, i.e., approximately 4 years after enrollment of the last study patient.

In addition, iDMC interim safety reviews occurred 3 months after the first patient was enrolled and 3 months after 500 patients were enrolled and followed up for safety.

Table 2 Analysis Timing

Analysis	Timing of Analysis
First iDMC review	At least 3 months after enrollment of the first patient
Second iDMC review	After 500 patients who reach at least 3-month follow-up
Optional / additional iDMC reviews	Defined by iDMC at any time during the study period
Primary analysis	6 months after the last patient has been enrolled
Final analysis	End of the study, i.e., approximately 4 (48 month) years after enrollment of the last study patient

3. STUDY CONDUCT

3.1 RANDOMIZATION ISSUES

Not applicable; study is not randomized.

3.2 INDEPENDENT REVIEW FACILITY

No IRF will be included in this study.

3.3 DATA MONITORING

The iDMC will share with the Sponsor the responsibility to monitor overall patient safety and/or efficacy of the Investigational Medicinal Product (IMP) with the objective to minimize patient exposure to unnecessary risk. The iDMC will notably review all AEs, SAEs and AEs of special interest and cumulative safety data including any death event during the scheduled interim analyses.

The details of the data summaries that will be produced for iDMC are described in the SAP on hand (required data for review by iDMC is outlined in the iDMC Charter).

4. STATISTICAL METHODS

Categorical data will be summarized in terms of the number of patients providing data at the relevant time point, frequency counts and percentages; 95% exact Clopper-Pearson CI will also be provided when relevant. Missing data will be considered when calculating percentages. Therefore, the percentages will be based on the total number of patients in the corresponding population and not on the number of non-missing values.

Unless otherwise specified, time periods are always calculated in months. If the duration is given in days, the number of days will be divided by 365.25 and multiplied by 12 to have the period shown in months.

Continuous data will be summarized using descriptive statistics. Missing data will not be imputed, unless otherwise stated. The number of observations being included as well as the number of missing observations will be given. Further the mean, standard deviation, median, lower (25%) and upper (75%) quartile, minimum and maximum will be used to describe the data. The minimum and maximum will be reported to the same number of decimal places as the raw data recorded in the database. The mean, median, lower and upper quartiles will be reported to one more decimal place than the raw data recorded in the database, and the standard deviation to two more decimal places.

Time to event data will be estimated by the Kaplan-Meier approach with the corresponding 95% CIs.

Two-sided 95% CIs for point estimates will be calculated and presented to one more decimal places than the raw data.

All outputs (tables, listings, figures) will be produced using the statistical analysis software SAS®, version 9.3 or higher. The generated outputs will be incorporated into a Microsoft® Word 2010 document using portrait or landscape orientation, whatever is appropriate, and afterwards printed to PDF.

Mapping of unscheduled visits:

In case of an unscheduled assessment prior to the date of first study drug administration, the unscheduled assessment will be assigned to the baseline visit.

In case of an unscheduled assessment after or on the date of first study drug administration, the unscheduled assessment will be assigned to the most recent visit performed.

If a patient has more than one assessment assigned to a same visit, the latest value assigned to the visit will be used, when presenting data in summary tables by visit. In listings by patient by visit all assessments (scheduled and unscheduled) will be presented.

Unscheduled visits will not be considered at all for tabulations of vital signs. In listings, these visits will appear as unscheduled without remapping.

Mapping of progression visits:

If the patient progresses, the visit where the first occurrence of tumor progression is recorded (earliest of the dates of the RECIST component indicating tumor progression) will be defined as the progression visit.

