## **2.4 BIOMARKER OBJECTIVES**

The biomarker objectives of the study are as follows:

- To evaluate PD-L1 prevalence based on retrospective evaluation of PD-L1 expression in tumor tissue measured by IHC. PD-L1 testing may be conducted on a subset of samples at local laboratories for inter-laboratory concordance evaluation
- To examine centrally assessed biomarkers and biomarker profiles in tumor tissue, and to correlate these with safety and/or efficacy outcomes. Biomarkers and biomarker profiles may be assessed using various methodologies including, but not limited to, IHC (single and multiplex, e.g., PD-L1 expression and immune cell infiltration analyses), RNA and DNA analysis (e.g., mutation and expression analyses)

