#### **4.1.1 Inclusion Criteria**

Patients must meet the following criteria for study entry:

1. Signed informed consent form
2. Age  $\geq$  18 years
3. Is, according to the investigator's judgment, able to comply with the study protocol
4. Histologically documented locally advanced (T4b, any N; or any T, N 2–3) or metastatic (M1, Stage IV) urothelial or non-urothelial carcinoma of the urinary tract
  - Urinary tract carcinoma includes carcinoma of the bladder, ureter, urethra, and renal pelvis
  - Primary non-urothelial carcinoma includes all sub-types listed in the WHO classification (see [Appendix 8](#))
    - Bellini collecting duct tumors are allowed if independently reviewed by two expert pathologists from different sites
    - Lymphoma, sarcoma, and renal cell carcinoma are excluded
5. Patients with measurable and/or non-measurable disease according to RECIST v1.1 are allowed
6. Must have progressed during or following treatment with at least one (and not more than 3) prior treatments for inoperable, locally advanced or metastatic urothelial or non-urothelial carcinoma of the urinary tract
  - Patients who received prior adjuvant/neoadjuvant chemotherapy and progressed within 12 months of treatment will be considered as having a first line of treatment for metastatic disease
  - Patients who were intolerant to prior systemic treatment are allowed as long as they had received at least 2 treatment cycles
  - Platinum- or non-platinum-based chemotherapy regimens are allowed
  - Low-dose chemotherapy given as radiosensitizer for curative treatment of localized disease does not count as a line of systemic chemotherapy
7. Representative formalin-fixed paraffin-embedded (FFPE) tumor specimen block available for submission.

- Only tissue from core needle (with  $\geq$  3 cores), punch, incisional, excisional, or forceps biopsies will be accepted. Fine-needle aspiration, brushing, bone tissue, and lavage samples are not acceptable
- If an appropriate tumor specimen is not available, a sample will be collected by biopsy during the study screening period
- ONLY at sites where local laws and regulations prohibit the sending of tumor specimen blocks to an outside central laboratory, specimen slides are acceptable. A minimum of 15 unstained serially-cut sections must be prepared and sent per tumor sample. For details, please refer to the Sample Handling Manual

8. Eastern Cooperative Oncology Group (ECOG) Performance Status 0, 1 or 2

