4.1 ANALYSIS POPULATIONS

In the study, two populations are distinguished: Safety Population and Intent-To-Treat (ITT) Population. The analysis for the iDMC will be provided based on the Safety Population.

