4.3 ANALYSIS OF BASELINE CHARACTERISTICS

Demography and baseline characteristics will be summarized using descriptive statistics and frequency tables, respectively, based on the safety population at Baseline.

A baseline value will be defined as the last available value before or on the date of first study drug administration, as follows:

- Assessment with a date prior to the date of first study drug administration
- Assessment with a date equal to the date of first study drug administration, if either
 - It is the screening/baseline visit
 - In case of assessments on the same date as the drug administration, it will be assumed that these were performed before the actual time of drug intake.

Demography:

- Descriptive statistics of age in years, age categories (<65, ≥65 -<85 and ≥85 years), age categories (<80 and ≥80 years)
- Frequency tables of sex, ethnicity and race

Baseline characteristics

- Non-cancer General Medical History
 - Number and percentages of patients with history of any medical condition overall and by status of medical condition and by System Organ Class (SOC) and Preferred Terms (PT)
- History of Cancer
 - Descriptive statistics of time from primary diagnosis to start of study treatment, frequency tables of histological tumor type, non-urothelial tumors sub-type, squamous neoplasms sub-type, glandular neoplasms sub-type, neuroendocrine sub-type, histological grade, location, TNM classification and stage of tumor at primary diagnosis and at study entry, descriptive statistics of time from primary diagnosis to diagnosis of metastatic disease
- Prior Tumor Surgery
 - Frequency of patients with prior tumor surgery before entering the study
 - Frequency tables of surgery setting and surgery purpose
- Prior Cancer Radiotherapy
 - Frequency tables therapy setting and given boost
- Prior Systemic Cancer Therapy
 - Frequency tables of therapy intent, highest line of therapy, and information regarding platinum treatment. Patients who received prior adjuvant/neoadjuvant chemotherapy will be considered as having 0 lines of treatment for metastatic disease (irrespective of the line(s) of therapy entered in eCRF).
- General Surgery and Procedure History (Non-Cancer)
 - Number and percentages of patients with any relevant surgeries or procedures
- Autoimmune disease
 - Number and percentages of patients who have any history of autoimmune disease

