 - PD-L1 expression by IHC class (IC0 to IC3)
 - PD-L1 expression: IC0/1 or IC2/3

Renal dialysis reported at baseline is defined as 'No' for all patients included with protocol version < 5 (regardless if any or no dialysis reported or no information given). For patients included with protocol version 5 or higher, if patient reports dialysis at Screening or Cycle 1 Day 1, then renal dialysis is set to 'Yes', otherwise if no dialysis is reported or if information is missing then renal dialysis is set to 'No'.

The time from diagnosis of primary disease to start of study treatment will be calculated in units of years as the difference between the date of start of study treatment and date of diagnosis of primary disease plus 1, divided by 365.25. For the calculation of the time from diagnosis of primary disease to start of study treatment, replacement rules will be applied in case the date of diagnosis of primary disease is incomplete. If day and month are missing, they will be imputed by June 30th to allow for time calculation, if only the day is missing, it will be imputed by 15. If after imputation, the date of diagnosis of primary disease is later than the start date of study treatment, then it will be set to the start date of study treatment.

The time from diagnosis of primary disease to diagnosis of metastatic disease will be calculated in units of years as the difference between the date of occurrence of metastatic disease and date of diagnosis of primary disease plus 1, divided by 365.25. For the calculation of the time from diagnosis of primary disease to diagnosis of metastatic disease, replacement rules will be applied for both dates in case dates are incomplete. If day and month are missing, they will be imputed by June 30th, if only the day is missing, it will be imputed by 15. If after imputation, the date of diagnosis of primary disease is later than the date of diagnosis of metastatic disease, then it will be set to the date of diagnosis of metastatic disease.

Creatinine clearance at baseline will be calculated using the Cockcroft-Gault formula:

$$\text{Creatinine clearance}[\text{mL / min}] = \frac{(140 - \text{age}[\text{years}]) \times \text{weight}[\text{kg}] \times (0.85 \text{ if female or } 1.0 \text{ if male})}{72 \times \text{serum creatinine}[\text{mg / dL}]}$$

A patient will be defined as having renal impairment in case creatinine clearance at baseline is < 30 mL/min.

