4.4.2.7 Utilities collected using the EQ-5D-5L for pharmacoconomic models

The EuroQol 5-Dimension Questionnaire (EQ-5D-5L) is a self-report health status questionnaire that consists of 6 questions used to calculate a health utility score for use in health economic analysis (Herdman et al 2011; Janssen et al 2013).

There are two components to the EuroQol EQ-5D:

- a five-item health state profile that assesses mobility, self-care, usual activities, pain/discomfort, and anxiety/depression,
- a visual analogue scale (VAS) that measures health state.

Overall scores range from 0 to 1, with low scores representing a higher level of dysfunction.

Country-specific, published utility functions would allow for creation of a single summary score for health-economic modelling. Such modelling is outside the scope of this SAP.

EQ-5D questionnaire compliance rate over time is calculated separately for each EQ-5D visit (Day 1 of first 3 study treatment cycles, then with tumor assessments) by using numbers of expected questionnaires as defined below:

- the expected number of EQ-5D questionnaires at a specific EQ-5D visit is either the
 - number of patients attending Day 1 visit of cycles 1, 2 or 3, respectively
 - number of patients attending a tumor assessment visit, respectively

Number of patients with expected questionnaires, all questions completed, at least one question completed and no question at all completed are summarized at each scheduled EQ-5D visit.

Summaries by visit, including changes from baseline, are provided for the EQ-D scores for

- each of the 5 dimensions
- the visual analogue scale

EQ-5D questionnaire will not be presented for primary analysis.

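### The full-population denominator in SAP 4 understates PD-L1 prevalence by the share of patients without an evaluable result

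*SAP*

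**What the plan says.** SAP section 4 (Statistical Methods) sets the general rule for categorical data. It opens: "Categorical data will be summarized in terms of the number of patients providing data at the relevant time point, frequency counts and percentages". Exact Clopper-Pearson 95% intervals are added when relevant. It then fixes the denominator: "the percentages will be based on the total number of patients in the corresponding population and not on the number of non-missing values".

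SAP 4.1 limits which population that can be: "two populations are distinguished: Safety Population and Intent-To-Treat (ITT) Population". There is no PD-L1-evaluable population.

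Protocol 2.4 states the objective: "To evaluate PD-L1 prevalence based on retrospective evaluation of PD-L1 expression in tumor tissue measured by IHC". The SAP output that estimates it is in section 4.3, where PD-L1 is tabulated by IC class (IC0 to IC3) and as IC0/1 against IC2/3, "based on the safety population at Baseline". No denominator specific to PD-L1 is given there. SAP 4.6.6 marks biomarker endpoints as not applicable, so no other section supplies a prevalence estimate.

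On tissue, Protocol 4.1.1 requires at entry a "Representative formalin-fixed paraffin-embedded (FFPE) tumor specimen block available for submission", with a screening biopsy if no suitable specimen exists, and slides where local law prevents shipping blocks. Neither document says how many samples are expected to be unevaluable.

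**The concern.** Counting missing as a non-event is defensible for adverse event incidence. It is also defensible for response, where Protocol 6.5 makes patients without a post-baseline tumour assessment non-responders. Prevalence has no such rationale, because an untested tumour has an unknown class. Under the SAP rule the four IC classes cannot add up to 100% unless every patient has a result, and each class is shrunk by the same factor.

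What is at stake is the only planned estimate of a stated objective. The table would report the proportion of patients who were tested and found IC2/3, under a label that will be read as the proportion who are IC2/3.

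The same denominator could also reach the pairwise associations in SAP 4.4.5, where PD-L1 IC2/3 is a listed subgroup. There the percentage in one subgroup, with an 80% Clopper-Pearson interval, is compared with the percentage in the whole population. If the share without a PD-L1 result differs between subgroups, that difference alone can generate a reported association.

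**Working it through.** **Check of the method.** The only precision figures in the documents are those in SAP Table 1. Exact Clopper-Pearson limits from beta quantiles reproduce all nine rows. For example, 5 of 1000 gives 0.16% to 1.16%, a half-width of 0.5%.

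**Inputs.** N = 1000 (the planned size in SAP 2.3, taken as the safety population). p = IC2/3 share among evaluable patients, assumed 30%. m = share without an evaluable result, assumed 5% to 20%. The documents give neither p nor m. As a rough check on p, the IC2/3 response interval in Protocol 1.3.3 (26%, 18% to 36%) fits an IC2/3 group of about 95 to 110 of the 310 patients: 95/310 = 30.6% and 110/310 = 35.5%.

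**Formula.** IC2/3 count x = p × N × (1 − m). The SAP rule prints x/N = p(1 − m). The evaluable denominator gives x/[N(1 − m)] = p. The relative understatement is 1 − (1 − m) = m, the same for every class and for any p.

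| m | x | SAP rule, x/1000 (95% CI) | Evaluable (95% CI) |
|---|---|---|---|
| 0% | 300 | 30.0% | 30.0% |
| 5% | 285 | 28.5% (25.7–31.4) | 285/950 = 30.0% (27.1–33.0) |
| 10% | 270 | 27.0% (24.3–29.9) | 270/900 = 30.0% (27.0–33.1) |
| 20% | 240 | 24.0% (21.4–26.8) | 240/800 = 30.0% (26.8–33.3) |

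At 10% missing, the full-population interval already excludes 30%. For assumed prevalences of 25%, 32% and 45%, exclusion begins at about 11%, 9% and 7% missing.

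**Associations (SAP 4.4.5).** Assume a subgroup of 300 with 25% missing, 10% missing overall, and 30% IC2/3 among evaluable patients in both.
- Overall on the SAP rule: 0.30 × 0.90 = 27.0%.
- Subgroup on the SAP rule: 300 × 0.75 × 0.30 = 67.5, taken as 68; 68/300 = 22.7%, upper 80% limit 26.1%. This is below 27.0%, so a negative association is reported.
- Subgroup on evaluable patients: 68/225 = 30.2%, 80% interval 26.2% to 34.5%. This contains 30.0%, so nothing is reported.

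**The case against.** The strongest reply is that the convention is disclosed and harmless. The same SAP paragraph reports the number of patients providing data, so the evaluable percentage and its exact interval follow from the printed count in one step. A reader might infer that a correct interval cannot be recovered from the output; that is not so. Tissue is mandatory at entry, so the missing share may be small. SAP 4 gives intervals only when relevant and does not name the PD-L1 table. The evaluable denominator also needs an assumption of its own, that having no result is unrelated to PD-L1 status.

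Most of this stands, and it limits the size of the point. It does not remove it. Submitting a block does not guarantee a scorable result, testing is retrospective, and a reader should not have to recompute the headline figure for a stated objective. The missingness assumption can be noted beside the estimate. The SAP figure equals population prevalence only if no unevaluable patient belongs to the class, which cannot hold for every class at once.

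Two wider readings are tempting, and the documents do not support them:

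- **By-visit results falling with dropout.** No by-visit categorical table is clearly planned. SAP 4.4.2.7 describes EQ-5D summaries for "each of the 5 dimensions" as scores with change from baseline, which suggests numeric summaries. Questionnaire compliance uses patients attending the visit.
- **Distorted laboratory shift tables.** SAP 4.6.3 sets baseline against worst on-treatment grade, not results by visit, and no bias in these tables has been shown here.

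**Conclusion.** The concern holds for PD-L1 prevalence. Following SAP 4 as written lowers every IC class in the SAP 4.3 table by a relative amount equal to the share without an evaluable result. With 30% IC2/3 among evaluable patients, that is 1.5, 3.0 or 6.0 percentage points at 5%, 10% or 20% missing, and zero if none are missing. The 30% and the missing shares are assumptions, so the actual size cannot be fixed from the documents. Reading the evaluable percentage as population prevalence further assumes that missingness is unrelated to PD-L1 status.

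The effect on the SAP 4.4.5 associations depends on that section using the same denominator and on missingness that differs between subgroups.

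A reader might infer that untested patients are classed as PD-L1 low and so contaminate the PD-L1 subgroup results. They fall in no class, the ratio of IC2/3 to IC0/1 is unchanged, and outcomes within the PD-L1 subgroups are not affected by this rule. No sample size, adverse event rate or response rate changes.

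**What to change.** In SAP 4 or 4.3, add that PD-L1 percentages and any confidence intervals are based on patients with an evaluable PD-L1 result, with the missing or not-evaluable count shown on its own line. Note that reading the result as population prevalence assumes missingness unrelated to PD-L1 status. In SAP 4.4.5, use the same denominator wherever PD-L1 IC2/3 is the characteristic being counted, both within the subgroup and in the whole population.

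Keep the full-population denominator for adverse event incidence and response. If EQ-5D levels are ever tabulated by visit, base them on patients with data at that visit.

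The cost is a few sentences and a denominator switch in the PD-L1 tables. No new data are needed. The trade-off is that the PD-L1 table then has a smaller n than the other baseline tables, which the separate missing count makes plain.
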